### **Purpose of the Study**

The purpose of this study is to determine if DuraDerm®, a medical device having novel technology, leads to a reduction in pin track infection rate (compared to the average prevalence reported in the literature) when applied as part of a pin track care protocol.

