### **Background**

Metal pins are commonly used for external fixation in research participants undergoing reconstructive or repair surgery. These pins protrude through the skin and create an avenue for migration of organisms. Anytime there is a break in the integrity of the skin, the risk of infection is increased. Pin site infections are a very common complication of external fixation, and unfortunately, the literature is scant on how to optimally minimize the risk of infection.

A Cochrane Collaboration Review published in 2004 to assess the effect on infection rates of different methods of cleaning and dressing orthopedic percutaneous pin sites determined that there was little evidence as to which pin site care regimen best reduces infection rates.

Depending on the reference, pin track infections rates have been reported to range from 0% to 100%. A systematic review of the incidence of pin track infections associated with external fixation published in 2016 revealed a cumulative pin track infection rate of 27%. This rate was defined as the inherent risk of any given research participant developing a pin track infection at a random pin or wire site during the course of treatment with external fixation. A 2016 review describes pin track infection as the most commonly expected problem, or even an almost inevitable complication, when using external fixation.

Several limitations of the current literature pose significant barriers to the study of pin site infection preventative strategies. Limitations include:

1. Lack of uniform definition/criteria to diagnose and classify severity of pin track infections. This makes it difficult to define the true incidence.
2. Highly variable control groups between studies. This creates difficulty in applying study results to an individual practice or protocol for preventative care.
3. Within studies, treatment groups often differ by more than one variable (e.g. ~~changing both the cleaning solution and dressing type~~). This makes it impossible

to determine the effect of individual variables and applying study results to an individual practice for protocol.

4. There exists few randomized controlled trials. This creates clinical practice based on low quality, underpowered, potentially biased studies.

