The Principle Investigator has utilized topically applied DuraDerm® as an additional step in his current treatment protocol for pin site care for several research participants (approximately 25) with over 200 pin sites with only 2 pin site infections. This represents a significant reduction from the average incidence of pin site infections reported in the literature (<1% vs 27% on a per research participant basis).

This study will be undertaken to formally evaluate whether DuraDerm® used on pin sites leads to a reduction in pin track infections when compared to the reported average incidence in the literature.

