## **Criteria for Research Participant Selection**

- 6 research participants with approximately 60 pin sites (average 10/research participant) will be enrolled into the study for the Control group receiving standard pin track care.
- 6 research participants with approximately 60 pin sites (average 10/research participant) will be enrolled into the study for the DuraDerm® group. These research participants will receive the exact same standard pin track care with the addition of DuraDerm® applied at each cleaning of the pin track area, as an additional step in the pin track care protocol.

The age of research participants was chosen based on the majority of principle investigator's research participants being adults and to avoid any special consideration that may apply to research with minors. The study will not be gender specific. There are no enrollment restrictions based upon race or ethnic origin. Study protocol will continue post discharge up to 6 to 8 weeks until patient final visit post pin removal. Proper inserving of product was conducted and documented.

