## **Methods and Procedures**

The study will enroll 12 total research participants (6 control research participants and 6 DuraDerm® research participants) with approximately 120 pin sites (approximately 60 in the Control group and 60 in the DuraDerm® group). Each research participant undergoing Deformity Correction and/or Traumatic Provisional Surgery will be asked to participate in the study to evaluate if the topical application of DuraDerm® as an additional step in the management of post-operative pin track site care reduces the incidence of pin track infections. Investigational Review Board (IRB) approval will be obtained and informed research participant consent will be obtained from each research participant.

For the control group, the usual care of pin track sites will be followed as outlined below (Pin Track Care Regimen). For the DuraDerm® group, the same care regimen will be followed with the addition of DuraDerm® applied topically to pin track site as the

experimental procedure being performed for research purposes. No additional tests or procedures outside of the existing standard regimen currently being utilized are anticipated.

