### **Potential Benefit to the Research participants**

Since the infection rate of pin track research participants is approximately 27%, and initial information provided by the principle investigator indicates a much lower pin track infection rate, the benefit of reduced infection appears to significant.

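### The protocol states its aim in two inconsistent ways, the comparison with the literature rate is never tested, and the prior-experience rate of under 1% is per pin but labelled per participant

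*Protocol*

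**What the plan says.** **Aim.** The protocol's Purpose of the Study asks whether DuraDerm "leads to a reduction in pin track infection rate (compared to the average prevalence reported in the literature"), and the end of the Background repeats that the study will evaluate whether it "leads to a reduction in pin track infections when compared to the reported average incidence in the literature". Methods and Procedures instead says that participants are asked to join to evaluate whether DuraDerm "as an additional step in the management of post-operative pin track site care reduces the incidence of pin track infections", with no literature comparator.

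**Design.** Criteria for Research Participant Selection enrols six participants who "will be enrolled into the study for the Control group receiving standard pin track care" and six who receive the same care plus DuraDerm. Data Analysis and Data Monitoring calls this an observational case series. The recruitment section calls it randomized, and the SAP report's introduction says that the six treated patients were randomly selected.

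**Analysis.** The protocol lists chi-square or Fisher tests of independence, with an open list of examples that names neither the group comparison nor a test against a reference rate. The SAP report poses the question as DuraDerm against Control and analyses only that: Fisher p = 0.45 for patients (Table 1) and chi-square p < 0.0001 for pins (Table 2).

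**Rates.** The Background defines the 27% as the "inherent risk of any given research participant developing a pin track infection at a random pin or wire site". It describes the investigator's experience in about 25 participants "with over 200 pin sites with only 2 pin site infections" and summarises it as "<1% vs 27% on a per research participant basis". Potential Benefit begins "Since the infection rate of pin track research participants is approximately 27" per cent.

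**The concern.** The aim that opens the protocol and closes its Background is not the question that the report answers. Neither document gives a test of any observed rate against 27%, or an interval set against it. Whether such a test could have succeeded depends on the unit, and the protocol is not consistent about the unit.

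The mislabelled prior rate errs in the device's favour. A per-pin rate under 1% is set beside 27% as if both counted participants, and Potential Benefit draws on the same experience to describe the expected gain.

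The design label matters because a case series has no comparison group, whereas the recruitment section and the report describe a randomized comparison. These points determine what the trial can claim to have shown.

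**Working it through.** **Inputs.** 27%, 2 infections, over 200 pins and about 25 participants (protocol Background); 6 vs 6 participants and about 60 pins per group (Methods and Procedures); 0/6 vs 2/6 patients, 0/60 vs 14/60 pins and alpha 0.05 with sidedness unstated (SAP report).

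**1. The report's own results reproduce.**
- Patients: with 2 infected of 12, the chance that both are controls is C(6,2)/C(12,2) = 15/66 = 0.227. Two-sided Fisher p = 30/66 = 0.45.
- Pins: Pearson chi-square = 15.85, p = 0.00007.
- Patient-level difference: 0/6 - 2/6 = -33 points, Newcombe 95% CI about -70 to +12.

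**2. Prior experience.**
- Per pin: 2/200 = 1.0%, hence under 1% with over 200 pins.
- Per participant: 1/25 = 4% if one person had both infections (exact 95% CI 0.1% to 20.4%), or 2/25 = 8% if two people had one each (1.0% to 26.0%).
- The stated figure reproduces per pin only.

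**3. The stated purpose, with 27% per participant.** Zero infections is the best possible result.
- One-sided p = 0.73^6 = 0.151. Two-sided exact binomial p = 0.200.
- Exact equal-tailed 95% upper limit = 1 - 0.025^(1/6) = 45.9%.
- Infection-free participants needed: 10 for one-sided p < 0.05 (0.73^9 = 0.059, 0.73^10 = 0.043); 11 by the two-sided exact binomial test (p = 0.043); 12 for the equal-tailed limit to fall below 27% (1 - 0.025^(1/12) = 26.5%; with 11 it is 28.5%).

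**4. The stated purpose, with 27% per pin.**
- Independent pins: one-sided p = 0.73^60 = 6 x 10^-9.
- Clustered pins, as illustration only. All 14 infected pins came from 2 control patients, and their split is not given. Assume 10 pins per patient and apply the controls' ANOVA ICC to the DuraDerm arm.
  - Split 7/7: between-patient mean square 1.307, within 0.078, ICC = (1.307 - 0.078)/(1.307 + 9 x 0.078) = 0.61.
  - Split 10/4: 1.667 and 0.044, ICC = 0.78.
  - Design effect 1 + 9 x ICC = 6.5 to 8.1, so 60 pins count as about 9.2 to 7.4. One-sided p = 0.73^9.2 to 0.73^7.4 = 0.055 to 0.096.
  - Beta-binomial with mean 0.27 and the same ICCs: chance of no infection among 10 pins is 0.499 to 0.606; to the sixth power, p = 0.015 to 0.049.

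**5. The two units are not interchangeable.** A per-pin rate of 27% with 10 independent pins implies 1 - 0.73^10 = 95.7% of participants infected. At the illustrative ICCs, the beta-binomial gives 1 - 0.499 = 50% down to 1 - 0.606 = 39%. None of these is 27%.

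**The case against.** The best defence is that the protocol does hold an aim that fits its design. Methods and Procedures asks whether adding DuraDerm reduces infections, next to two concurrent groups, and the report follows that aim. A concurrent control is the stronger comparison and does not rule out a literature comparison as well. This stands: the fault is inconsistent aims, not a design unsuited to every stated aim.

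The report also never mentions 27% or any literature rate. A reader might infer from its statement of a 97% lower risk that a reduction against the literature was shown, but the report does not claim it; its tables, tests and risk ratio all compare DuraDerm with Control.

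On units, the Background itself warns that the literature mixes per-patient and per-pin rates, and the cited review cannot be checked here. What stands is the internal inconsistency. The definition reads most naturally as per pin, while the later uses are per participant.

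A reader might also infer that the mislabelled rate drove the SAP report's requirement of 33 patients per group. That number fits 27% vs 0.5% with a continuity correction (two-sided 0.05, 80% power), but the report does not state its input rates, so this remains conjecture.

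Finally, the report already gives the patient-level result first and calls it severely under-powered. That is to its credit, although its positive finding rests on the pin-level test.

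**Conclusion.** The point holds as one of inconsistent aims, a mislabelled rate and contradictory design labels. The purpose in the opening section and the Background is unanswered. On the participant unit it could not have been answered with six treated participants: even 0/6 gives one-sided p = 0.15 and an upper limit of 46%. The prior experience is 4% to 8% of participants, taking exactly 25 participants and the 2 infections in one or two people.

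A reader might infer that the choice of comparator makes no difference. That is not supported. In the illustrative beta-binomial model, 0/60 against 27% per pin gives one-sided p of 0.015 to 0.049, while the patient-level comparison with Control gives 0.45 (0.23 one-sided). Nor can one infer that 27% per pin means that almost every participant is infected: 95.7% needs independent pins. The clustered figures rest on two infected controls with an unknown split, 10 pins each, and an ICC carried to an arm with no infections; they are not estimates.

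The pin-level p < 0.0001 depends on the report's assumption that pins are independent. The patient-level result does not, and should lead. The change should be made, but it alters what is claimed rather than any reported test.

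**What to change.** 1. Leave the original aim visible. Add a dated note, disclosed as post hoc because the report was written after the data, such as: *The comparison made is with concurrent participants receiving the same pin care without DuraDerm. No test against the literature rate was done and none is claimed.*
2. In the Background, give the prior experience in one unit at a time: 2 of over 200 pins; 1 or 2 of about 25 participants, whichever the records show.
3. Wherever the 27% appears, keep it as context only and state its unit after checking the cited review.
4. In Data Analysis and Data Monitoring, replace the case-series label with a controlled design label. Use *randomised* only if allocation was random, and then state the method.
5. Lead the report's conclusion with the patient-level difference and interval from step 1 of the working, described as descriptive. Say that all 14 infected pins came from 2 control patients and that the pin-level p-value assumes independent pins.

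**Cost.** Wording only, with no new patients or procedures. The claim against the literature rate is given up, and choosing the lead analysis now is itself post hoc. No power is gained: with 6 vs 6, two-sided Fisher needs 0/6 vs at least 5/6 (p = 0.015; 0/6 vs 4/6 gives 0.061). Power is about 0.5% at an assumed 27% vs 4%, and 0.4% at 27% vs 8%, taking 27% as per participant.

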### **Background**

Metal pins are commonly used for external fixation in research participants undergoing reconstructive or repair surgery. These pins protrude through the skin and create an avenue for migration of organisms. Anytime there is a break in the integrity of the skin, the risk of infection is increased. Pin site infections are a very common complication of external fixation, and unfortunately, the literature is scant on how to optimally minimize the risk of infection.

A Cochrane Collaboration Review published in 2004 to assess the effect on infection rates of different methods of cleaning and dressing orthopedic percutaneous pin sites determined that there was little evidence as to which pin site care regimen best reduces infection rates.

Depending on the reference, pin track infections rates have been reported to range from 0% to 100%. A systematic review of the incidence of pin track infections associated with external fixation published in 2016 revealed a cumulative pin track infection rate of 27%. This rate was defined as the inherent risk of any given research participant developing a pin track infection at a random pin or wire site during the course of treatment with external fixation. A 2016 review describes pin track infection as the most commonly expected problem, or even an almost inevitable complication, when using external fixation.

Several limitations of the current literature pose significant barriers to the study of pin site infection preventative strategies. Limitations include:

1. Lack of uniform definition/criteria to diagnose and classify severity of pin track infections. This makes it difficult to define the true incidence.
2. Highly variable control groups between studies. This creates difficulty in applying study results to an individual practice or protocol for preventative care.
3. Within studies, treatment groups often differ by more than one variable (e.g. ~~changing both the cleaning solution and dressing type~~). This makes it impossible

to determine the effect of individual variables and applying study results to an individual practice for protocol.

4. There exists few randomized controlled trials. This creates clinical practice based on low quality, underpowered, potentially biased studies.
5. There is no consistency in reporting infection rate (per patient vs per individual pin site). This creates difficulty in studying incidence, comparing studies, or conducting an accurate meta-analysis.

Research participants eligible for the study will be those undergoing Deformity Correction and Traumatic Provisional Fixation. These research participants have a number of pins placed to ensure this required rigid fixation. The number of external fixation pins averages approximately ten per research participant.

DuraDerm® is a 510K FDA cleared medical device indicated for providing a covering over minor wounds and scrapes that are clean and dry. The microbicidal liquid solution consists of organic polymer dissolved in methylene chloride organic solvent. The unique formulation eradicates any organisms (bacteria, fungi, viruses) it comes in contact with. This is a result of the methylene chloride's activity against an infinite number of organisms. The methylene chloride evaporates leaving a clear, elastomeric, non-odorous film for covering minor wounds. The film protects the wound against entry of water, dirt, and germs. The film is elastomeric and protects in difficult regions where flexing, bending and creasing skin occurs. The clear film forms in less than a minute. Application is commonly accomplished using a cotton tip applicator. The liquid is applied on and around the wound extending at least an inch and a quarter beyond the edges of the wound. Momentary stinging may occur upon initial application. The film commonly remains intact for one to three days or longer depending on exposure to rubbing, flexing, or soap and water. This film is resistant to degradation by water alone, but can be easily removed with the combination of soap and water or it can be gently peeled off starting at the outer edges. DuraDerm® is for external use only. DuraDerm® is not intended for use on deep or infected wounds or puncture wounds, or for use near the eyes, mouth, or nose. Intentional inhaling of the contents may be harmful or fatal. The bottle should be tightly capped after each use to prevent evaporation of the solvent.

The Principle Investigator has utilized topically applied DuraDerm® as an additional step in his current treatment protocol for pin site care for several research participants (approximately 25) with over 200 pin sites with only 2 pin site infections. This represents a significant reduction from the average incidence of pin site infections reported in the literature (<1% vs 27% on a per research participant basis).

This study will be undertaken to formally evaluate whether DuraDerm® used on pin sites leads to a reduction in pin track infections when compared to the reported average incidence in the literature.

## **Criteria for Research Participant Selection**

- 6 research participants with approximately 60 pin sites (average 10/research participant) will be enrolled into the study for the Control group receiving standard pin track care.
- 6 research participants with approximately 60 pin sites (average 10/research participant) will be enrolled into the study for the DuraDerm® group. These research participants will receive the exact same standard pin track care with the addition of DuraDerm® applied at each cleaning of the pin track area, as an additional step in the pin track care protocol.

The age of research participants was chosen based on the majority of principle investigator's research participants being adults and to avoid any special consideration that may apply to research with minors. The study will not be gender specific. There are no enrollment restrictions based upon race or ethnic origin. Study protocol will continue post discharge up to 6 to 8 weeks until patient final visit post pin removal. Proper inserving of product was conducted and documented.

### **Inclusion Criteria:**

1. Deformity correction, traumatic provisional fixation
2. All pin sites are stable
3. 18 years of age or greater
4. No known contraindication to receive DuraDerm®

### **Exclusion Criteria:**

1. Age less than 18 years
2. Known allergy to Methylene Chloride
3. Known sensitivity to organic polymers
4. Non-clean, dry wound at pin
5. Vulnerable research participants (Institutionalized, students, employees, prisoners, or those with decisional incapacity, etc.)

## **Methods and Procedures**

The study will enroll 12 total research participants (6 control research participants and 6 DuraDerm® research participants) with approximately 120 pin sites (approximately 60 in the Control group and 60 in the DuraDerm® group). Each research participant undergoing Deformity Correction and/or Traumatic Provisional Surgery will be asked to participate in the study to evaluate if the topical application of DuraDerm® as an additional step in the management of post-operative pin track site care reduces the incidence of pin track infections. Investigational Review Board (IRB) approval will be obtained and informed research participant consent will be obtained from each research participant.

For the control group, the usual care of pin track sites will be followed as outlined below (Pin Track Care Regimen). For the DuraDerm® group, the same care regimen will be followed with the addition of DuraDerm® applied topically to pin track site as the

experimental procedure being performed for research purposes. No additional tests or procedures outside of the existing standard regimen currently being utilized are anticipated.

## **Pin Track Care Regimen**

### **Control and DuraDerm® Groups**

All pins and wire sites will be cleaned daily while hospitalized. Basic pin care will be performed once daily by hospital nursing staff prior to discharge. Following discharge from the hospital, the pin care protocol will be continued by research participant's caregiver.

Ideally, pin sites are cleaned when the surrounding skin and gauze are soft. This should make removal of gauze and cleaning of pins less painful. The purpose of the cleaning is to prevent the skin from attaching to the pins and wires and to decrease the chance of infection, as well as, inspect the area for any signs of infection.

Research participants will be instructed to notify the Principal Investigator if they observe any signs or symptoms of infection. These include redness around pin site, discharge, tenderness in the soft tissue, loosening of the pin, nausea, vomiting, fever or chills.

Research participants will be instructed that the approach to pin care should occur in a step-wise fashion. If Step 1 is effective there is no need for further debris removal and research participants will be instructed conclude the care protocol (Control Group) or proceed to Step 3 (DuraDerm® group). Basically, if Step 1 removes all debris, Steps 2 is not necessary. It is not uncommon for all of Steps 1 and 2 to be needed to completely remove debris.

Step 1:      Brush the pin sites with saline using an ordinary soft toothbrush or gauze with sterile gloves

Step 2:      If following Step 1, debris remains, use forceps (tweezers) to gently remove debris.

